Aim 1: Demonstrate that 5-HT_{1b} activation reduces the reinforcing effects of cocaine. The primary hypotheses, related to our first specific aim, are that: 1) cocaine will function as a reinforcer on the concurrent progressive-ratio choice task that was developed and validated in our laboratory ([name] et al., 2016; 2020) and 2) zolmitriptan will attenuate the reinforcing effects of cocaine, leading to the reallocation of behavior towards the non-drug alternative (i.e., \$6.00) available on the choice task.

Aim 2: Demonstrate that 5-HT_{1b} activation attenuates subjective abuse-related effects of cocaine (e.g., positive subjective effects, craving). The primary hypotheses related to our second specific aim are that: 1) cocaine will produce prototypic effects on subjective outcomes (e.g., increased ratings of drug liking) and 2) zolmitriptan will attenuate these effects (e.g., reduce cocaine related increases on ratings of drug liking).

Aim 3: Demonstrate that 5-HT_{1b} activation attenuates impulsive responding that is a common characteristic of cocaine use disorder and is mediated by the 5-HT system. The primary hypothesis related to our third specific aim is that zolmitriptan will attenuate impulsive responding (e.g., reduce delay discounting of drug and money). This hypothesis is based upon our previous findings and the preclinical outcomes described above.

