Cognitive Outcomes. Four cognitive-behavioral measures that evaluate impulsive behavior will be included and will be completed 20 minutes after administration of the sampling dose. These tasks were selected because: (i) cocaine users display increased impulsive behavior (Coffey et al., 2003; Fillmore and [name], 2002; Heil et al., 2006; Liu et al., 2011) which likely contributes to poor treatment response and relapse (Dalley et al., 2011; Poling et al., 2007) and (ii) 5-HT systems are strongly implicated in impulsive behavior (Brunner and Hen, 1997; Cunningham and Anastasio, 2014; Howell and Cunningham, 2015). The selected tasks measure three key, independent aspects of impulsivity: impulsive decision-making (i.e., delay discounting for money and cocaine), impulsive inattention (i.e., n-Back), and impulsive disinhibition (i.e., go/stop task) (Reynolds et al., 2008). Tasks will be completed in random order across subjects, but the order of tasks will remain consistent for each subject.

Hypothetical Delay Discounting (Appendix B). A 5-trial adjusting delay discounting task will be used to rapidly assess discounting rates for various commodities (Koffarnus and Bickel, 2014). In this task, subjects making a series of 5 choices between an immediately available, smaller reinforcer and a larger reinforcer at various delays. Versions of this task with monetary (e.g., \$1000 delayed versus \$500 now) and cocaine (e.g., \$1000 of cocaine delayed versus \$500 of cocaine now) commodities will be used. Subjects will be told that all choices are hypothetical. The primary outcome of this task is the discounting rate (k). Previous research has demonstrated that this measure provides rapid and accurate discounting rates across a range of commodities (Cox and Dallery, 2016; Koffarnus and Bickel, 2014; Strickland et al., 2017).

n-Back (Appendix C). The n-Back task will be used to measure working memory and working memory capacity (Jaeggi et al. 2010). In this task, subjects are presented with a sequence of numbers and asked to indicate when the current stimulus matches the one from “n” steps earlier. Two settings will be used in this study, the 1-back and the 2-back (i.e., matching 1 and 2 stimuli back, respectively). The primary outcome of this task is the percentage of correct responses.

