Stop-Signal Task. Letters (X or O) will be presented on the screen one at a time and participants are instructed to respond on the computer keyboard to identify the letter that was presented. On approximately 30% of trials a stop-signal tone (a 500 ms, 900 Hz tone) will occur, and participants must withhold their response (50 trials). The tone will be random and will occur at one of five delays (10, 70, 150, 230, or 300 ms; stop-signal delay) after the presentation of the letter. The presentation of the stop-signal is divided evenly between letters. Participants are instructed to respond as quickly as possible to letters and not to wait for the tone to occur. The dependent variables from the stop-signal task are the mean proportion of inhibitory failures to the stop-signal and by the estimated mean latency to inhibit a response. The mean RT to the go-signals (i.e., responding to the letters, not in the presence of the stop-signal) will measure response execution to go-signals during a test (i.e. the average time from the onset of letter presentation until a computer key press). Shorter reaction times (i.e. faster responding) indicate greater response execution. The inhibition and execution measures are highly reliable across trials (alpha coefficients >0.90) and stable over sessions (test-retest reliabilities >0.85) in both drug-using and non-drug-using populations (Fillmore and [name], 2001; Fillmore and Vogel-Sprott, 1999; Mulvihill et al., 1997). The order of letters, stop-signal, and stop-signal delays will be random.

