Data Analysis. All data will be analyzed statistically as outlined below using SPSS. Only data from completing subjects will be included in the analyses. Any subjects who do not complete the study will be replaced until we accrue 20 completers. Statistical significance refers to $p \leq 0.05$.

Aim 1: Demonstrate that 5-HT_{1b} activation reduces the reinforcing effects of cocaine. The reinforcing effects of cocaine will be determined by evaluation of break points for cocaine and money from the concurrent progressive-ratio choice task. For cocaine and money break points, each of which have one data point for each dose condition, data will be analyzed using two-factor repeated-measures ANOVA. Cocaine (0, 10, and 30 mg/70 kg) and zolmitriptan (0, 2.5, 5, and 10 mg/day) will be factors for these analyses. A significant augmentation (i.e., leftward shift in the dose-response curve) or attenuation (i.e., rightward shift in the dose-response curve) of the effects of cocaine will be inferred if the main effect of the zolmitriptan or the cocaine-zolmitriptan interaction attains statistical significance in the ANOVA. If the cocaine-zolmitriptan interaction attains statistical significance, the Mean Square Error (MSE) term will be used to conduct Tukey's HSD *post-hoc* test to make appropriate pair-wise comparisons between means.

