Aim 2: Demonstrate that 5-HT_{1b} activation attenuates subjective abuse-related effects of cocaine (e.g., positive subjective effects, craving). Three sets of analyses will be conducted on the subjective effect data. First, data will be analyzed as peak effect (i.e., maximum effect observed following administration of cocaine sampling doses) using two-factor repeated-measures ANOVA. Cocaine (0, 10, and 30 mg/70 kg) and zolmitriptan (0, 2.5, 5, and 10 mg/day) will be factors for these analyses. A significant augmentation or attenuation of the effects of cocaine will be inferred if the main effect of the zolmitriptan or the cocaine-zolmitriptan interaction attains statistical significance in the ANOVA. If the cocaine-zolmitriptan interaction attains statistical significance, the MSE term will be used to conduct Tukey's HSD *post-hoc* test to make appropriate pair-wise comparisons between means. Second, Area Under the Curve (AUC) will be calculated for each subject using the trapezoidal method and analyzed in the same fashion as peak-effect data. Third, these data will be analyzed by repeated-measure ANOVA with cocaine, zolmitriptan and time as factors. The MSE term for the cocaine-zolmitriptan-time interaction will then be used to conduct Tukey's *post-hoc* tests to make appropriate pair-wise comparisons.

Aim 3: Demonstrate that 5-HT_{1b} activation attenuates impulsive responding that is a common characteristic of cocaine use disorder and is mediated by the 5-HT system. For the impulsivity outcomes, each of which have only one data point for each dose condition, data will be analyzed using two-factor repeated-measures ANOVA. Cocaine (0, 10, and 30 mg/70 kg) and zolmitriptan (0, 2.5, 5, and 10 mg/day) will be factors for these analyses. A significant augmentation or attenuation of the effects of cocaine will be inferred if the main effect of the zolmitriptan or the cocaine-zolmitriptan interaction attains statistical significance in the ANOVA. If the cocaine-zolmitriptan interaction attains statistical significance, the MSE term will be used to conduct Tukey's HSD *post-hoc* test to make appropriate pair-wise comparisons between means.

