17. DATA AND SAFETY MONITORING

Data Monitoring Plan

Data will be collected using a computerized data collection and management system wherever possible. This system automates the collection of data, which ensures the accuracy and completeness of data collection. The data are stored in a unique file on the hard drive of the computer and are printed after all the tasks are completed. In all instances, the data files do not contain the name of the subject, but instead, a unique four-digit number identifies each subject. A computer file linking the unique number with the subject's name will be kept on a stand-alone, password-protected computer. All data requiring hand entry (e.g., cardiovascular measures) will be double entered by two separate staff members and comparison macros run to ensure accuracy. Data files for experimental tasks and physiological measures from each experimental session will be manipulated and combined into a single electronic spreadsheet for each subject by the PI. Data for all subjects will then be combined into a single electronic spreadsheet and separated by experimental measure for statistical analysis.

The primary outcomes will be the break points for drug and money in the cocaine self-administration task, analyzed as a function of zolmitriptan maintenance conditions. Secondary outcome measures will be abuse-related subjective and cognitive effects of cocaine, analyzed as a function of zolmitriptan maintenance conditions. Tertiary outcome measures will be the physiological and side-effects of cocaine, analyzed as a function of zolmitriptan maintenance conditions. Data will be analyzed using repeated measure ANOVA. The alpha level will be set at 5%.

As noted above, wherever possible, data are collected using an automated computer system, which increases the accuracy and completeness of data collection and ensures the validity and integrity of the data. The initial data manipulation described above will be conducted twice and compared. The quality of manipulated data and data analyses will be monitored by random inspection by the PI and/or Co-Investigators.

Safety Monitoring Plan

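### The Aim 3 rule draws a conclusion about cocaine's effects when the hypothesis concerns impulsive responding, sets no direction after a main effect, and leaves several secondary outcomes unordered at an unadjusted 5%

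*Combined protocol and SAP*

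**What the plan says.** Section 1 gives Aim 3 a single hypothesis: "zolmitriptan will attenuate impulsive responding (e.g., reduce delay discounting of drug and money"). Delay discounting is an example there, not a designated outcome. Aims 1 and 2 each have two hypotheses, one that cocaine has an effect and one that zolmitriptan reduces it. Aim 3 predicts no cocaine effect.

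Section 7, Cognitive Outcomes, lists four measures and says "The selected tasks measure three key, independent aspects of impulsivity". It names k as the main result of the discounting task, which is run for money and for cocaine. For n-Back, run at 1-back and 2-back, it names percent correct. The stop-signal task has as dependent variables "the mean proportion of inhibitory failures to the stop-signal and by the estimated mean latency to inhibit a response", and go reaction time is also recorded.

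Section 7, Data Analysis, Aim 3, applies one 3 × 4 within-subject ANOVA to each outcome: "For the impulsivity outcomes, each of which have only one data point for each dose condition, data will be analyzed using two-factor repeated-measures ANOVA". The conclusion allowed is "A significant augmentation or attenuation of the effects of cocaine will be inferred". Either of two tests is enough to trigger it, since the condition given is "if the main effect of the zolmitriptan or the cocaine-zolmitriptan interaction attains statistical significance in the ANOVA". Tukey's HSD follows only if the interaction is significant.

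Section 17 ranks break points as primary, subjective and cognitive effects of cocaine as secondary, and physiological and side effects as tertiary. It adds: "The alpha level will be set at 5" per cent. Nothing orders the Aim 3 outcomes among themselves, says how many must be positive, or adjusts for their number.

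**The concern.** There are two separate problems.

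First, the inference does not match the hypothesis. The rule's wording suits Aims 1 and 2, where a cocaine effect is predicted and zolmitriptan is expected to reduce it. For Aim 3 the quantity of interest is the level of impulsive responding, which the zolmitriptan main effect addresses. The rule turns that main effect into a statement about cocaine. It also accepts a change in either direction, with no planned comparison after a significant main effect to separate less impulsivity from more.

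Second, two F tests on each of several outcomes, all at 5%, leave open which result speaks for the aim. The aim is worded as a demonstration. A report could rest on one significant F while the other aspects of impulsivity were flat or moved the other way, and nothing written beforehand would say whether that counts.

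**Working it through.** **1. The plan's own figure.** The documents give no Aim 3 error rate; the only related number is 80% power at f = 0.27 with 20 completers (Section 7, Power Analysis). For a four-level within-subject factor, assuming sphericity and a correlation of 0.5 between repeated measures (neither is stated), λ = f²·n·m/(1 − ρ) = 0.27² × 20 × 4 / 0.5 = 11.66 on 3 and 57 df. Power is 79.9%, so the figure reproduces. Treating the 12 cells as one factor with ρ = 0 also gives 79.7%, so the exact basis cannot be identified. Either way it is one test on one outcome at an unadjusted 5%.

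**2. What the rule concludes.** Let μ(c,z) be the mean at cocaine dose c and zolmitriptan dose z. Cocaine's effect at z is μ(c,z) − μ(0,z). Suppose zolmitriptan lowers the outcome by the same δ(z) at every cocaine dose, so μ(c,z) = μ(c,0) − δ(z). Then μ(c,z) − μ(0,z) = μ(c,0) − μ(0,0): cocaine's effect is unchanged. The Aim 3 hypothesis is nevertheless true, and the main effect can be significant with no interaction. The rule would report an altered cocaine effect. If δ(z) were negative (more impulsivity), the same F test would be significant, and no planned comparison would give the direction.

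**3. Counting outcomes.** From Section 7: k for money, k for cocaine, percent correct at 1-back and at 2-back, inhibitory failures and stopping latency make six. This is a count from the text, not a number the plan gives. Reading the plan as four measures gives four; adding go reaction time gives seven.

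**4. Independent outcomes, no true effect.**
- One outcome, both F tests: 1 − 0.95² = 9.75%.
- Six outcomes, both tests, either direction: 1 − 0.95¹² = 46.0%.
- Six outcomes, both tests, attenuating direction: by symmetry 0.0975/2 per outcome, so 1 − (1 − 0.04875)⁶ = 25.9%.
- Six outcomes, main effect only, attenuating direction: 1 − 0.975⁶ = 14.1%.
- Four outcomes, both tests, either direction: 1 − 0.95⁸ = 33.7%.
- Seven outcomes, both tests, either direction: 1 − 0.95¹⁴ = 51.2%.

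**5. Correlated outcomes.** Simulation under the global null used 20 subjects, 3 × 4 cells and sphericity, with equal correlation r between outcomes, F(3,57) for the main effect and F(6,114) for the interaction. Attenuating means that the pooled active-dose mean is better than the 0 mg/day mean.

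| Six outcomes | r = 0 | r = 0.5 | r = 0.8 |
|---|---|---|---|
| Any significant F, either direction | 46.6% | 38.7% | 27.6% |
| Any significant F, attenuating direction | 26.2% | 20.6% | 15.0% |
| Main effect only, attenuating direction | 14% | 11% | 8% |

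Repeat runs differ by about one percentage point, which is why the top of the first two ranges is given as 47% and 27%. At r = 0.9 the first row falls to about 21%. With four outcomes, either direction, the rate is about 22–23% at r = 0.8 and 33–34% at r = 0.

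**The case against.** The strongest reply is that a reader might take 28–47% as the chance of a false Aim 3 claim. The documents do not support that. The figure counts augmentation as well as attenuation, and the aim claims only attenuation. The rule reads as applying to each outcome's ANOVA; no passage says that one positive outcome establishes the aim. On the test closest to the hypothesis, the main effect in the right direction, the figure is about 8–14%. The number of outcomes and the correlations are also assumptions. Calling the aspects independent describes constructs and does not state zero statistical correlation. All of this stands and sets how the figures should be read.

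A second reply is that the cocaine wording is deliberate. Section 17 describes these outcomes as cognitive effects of cocaine, and Section 7 places the tasks 20 minutes after the sampling dose. This stands in part. If zolmitriptan reduced impulsivity only after active cocaine, the interaction is where that would show, so it would be wrong to infer that the interaction is irrelevant to Aim 3. But the reply does not rescue an inference about cocaine's effects drawn from a main effect alone.

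A third reply is that these are secondary outcomes in a small laboratory study, where formal family-wise control is partly a matter of preference. That limits the priority. It does not touch the mismatch between rule and hypothesis, which would remain with a single outcome. Nor is Aim 3 marked exploratory, a label the plan does use for its biological-variable analyses.

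**Conclusion.** The concern holds as a point about secondary outcomes. The mismatch in the inference rule and the missing direction check follow from the text and need no numerical assumption.

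The multiplicity part rests on a count of six outcomes, correlations of 0 to 0.8, sphericity and no true zolmitriptan effect. On those terms the chance of at least one significant F is about 28–47% in either direction, about 15–27% in the attenuating direction, and about 8–14% from main effects in that direction. Only the last two describe a result that could be read as support for the aim, and only if one positive outcome were treated as enough, a question on which the plan is silent.

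Two further readings go beyond the documents. The primary result is not compromised, because Section 17 places break points in their own tier. Cocaine discounting is not already the designated Aim 3 outcome, because Section 1 cites drug and money discounting together, as an example.

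**What to change.** In Section 7, Data Analysis, give Aim 3 its own rule:

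- Infer a change in impulsive responding from the zolmitriptan main effect.
- Claim attenuation only if planned comparisons of the active doses with 0 mg/day show less impulsive responding: lower k, fewer inhibitory failures, shorter stopping latency, or higher n-Back percent correct.
- Infer a change in cocaine's effect on impulsivity only from the interaction.
- Before analysis, either name the deciding outcome or outcomes (for example the two discounting rates cited in Section 1), apply Holm across them and label the rest supportive, or apply Holm across all Aim 3 outcomes. State whether the interactions belong to the same Holm family.

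This takes a few sentences and needs no new data or subjects. The cost is power for individual secondary outcomes. In the calculation of step 1 (f = 0.27, λ = 11.66), Holm's strictest step is 0.05/2 = 0.025 for two outcomes and 0.05/6 = 0.0083 for six. Power at that step falls from 80% to about 71% and 55%, and the effect detectable with 80% power rises from f = 0.27 to about 0.30 and 0.33. Naming two outcomes therefore costs less than covering all six. A finding on an outcome not named would count as supportive only.
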